There is substantial evidence that the mammalian spinal cord utilizes autonomous oscillating interneuronal circuits (central pattern generators, CPG) that respond to afferent input to generate locomotion [7-16]. The importance of afferent input in modulating and maintaining these neural locomotor patterns has been abundantly documented, and a completely spinal cord transected animal can relearn to hindlimb step and stand with task specific training that uses the critical sensory cues needed for each task [17-25]. Further, a myriad of reflexes are modulated in amplitude and even reversed by afferent input during different phases of the stepping cycle and CPG networks modulate these reflex pathways during locomotion [16, 26-42]. The human spinal networks use the sensory input during stepping to generate functionally relevant efferent output and, after minutes of manual assistance, can generate a series of independent steps. Also, brief standing with full weight bearing can be executed after weeks of stand training, again without SCES [43]. However, the independence of standing and stepping is not sustainable to allow a transition to walking overground [44].

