We propose that daily locomotor training in the presence of SCES will enable the individual with clinically complete SCI to stand and step independently while bearing full weight. Non-patterned electrical stimulation of the lumbar spinal cord can induce patterned, locomotor-like activity in individuals with clinically complete SCI [1]. Modifying the frequency of stimulation can induce extensor patterns similar to that observed during standing [45]. In addition, when afferent information is also provided there is further modulation of these motor patterns elicited by epidural stimulation [46]. Individuals with a clinically complete spinal cord injury can execute independent steps using a body weight support system on a treadmill (BWST) using manual assistance without epidural stimulation. When combined with SCES, we anticipate the training will be even more successful, enabling prolonged periods of independent stepping and standing. Although there will not be a separate control group studied simultaneously, historical controls will consist of the best stepping and standing performance that have been observed previously in our laboratory in individuals that have a clinically complete SCI. Performance beyond this threshold by any individual treated with both epidural stimulation and training will be interpreted as a significantly better intervention than training alone.

Future studies will eventually focus on development and implementation of the more advanced multi-electrode array technique that will provide functionally-adaptive site-specific stimulation. The adaptive stimulation strategy proposed here takes advantage of capabilities of our new array design that are not possible using either conventional or commercially available electrode arrays. Our future arrays will provide two key benefits:

- Our electrode arrays cover a larger area than commercially available arrays, extending from the midthoracic to the sacral extents of the spinal cord. It is possible that the optimal stimulation sites for facilitating stepping versus standing may be spatially distinct on the spinal cord. If this is the case, conventional arrays are less likely to be able to recover both stepping and standing in the same patient.

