- Numerous findings suggest that locomotor training may progressively change the state of the spinal networks that are responsible for stepping and standing. Therefore, the optimal sites for stimulating these motor tasks may migrate over the course of treatment. The adaptive algorithm that we propose will track the optimal sites for stimulation weekly and, using this information, we will select electrode(s) from our array that generates the most successful standing or stepping. An electrode array will allow us to precisely target the most effective stimulation sites.

A couple of recent studies have shown the ability to produce stepping following complete transactions in adult rats when stimulating at the S1 level [65, 66]. Therefore we propose the implantation of 2 stimulating electrodes to cover a broader area of the human spinal cord.

B. Objectives of the research

The overall aim is to assess whether task specific locomotor training and SCES can induce neural reorganization of the functionally isolated human spinal cord to improve standing and stepping in individuals with functionally complete SCI. We propose that locomotor training will result in generation of more effective standing and stepping efferent patterns by restoring phase dependent modulation of reflexes and reciprocal inhibition,

reducing clonus and mediating interlimb coordination. We propose that the SCES will optimize the physiological state of the spinal cord interneuronal circuitry compromised by compensating for loss of supraspinal input for the retraining of these tasks.

The proposed studies will allow us to gather critical information using commercially available electrodes to design the more advanced multi-electrode array technique that will be adaptive and conceivably be effective in a wider range of patient populations. The current electrodes used in this study will serve two objectives: 1) to improve standing and stepping with the combination of epidural stimulation and locomotor training in individuals with functionally complete SCI; and 2) to provide critical information for the development of more advanced electrodes.

C. Significance of the research

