and discontinue their participation at any time without penalty. [name] will answer any questions with the potential research participant and/or family members who may have a relationship with them regarding the physical rehabilitative aspects of the research.

[name] or [name] will discuss the surgical protocols and the risks and benefits with the potential research participant. They will verbally review the surgical procedures and show the individual the stimulating and recording equipment that will be implanted. [name] or [name] will review all testing that will be conducted during the surgical procedures and explain to the potential research participant that s/he can refuse any of the procedures and discontinue their participation at any time without penalty. [name] or [name] will answer any questions with the potential research participant and/or family members who may have a relationship with them regarding the surgical procedures and the research.

[name] will determine study eligibility based on the inclusion and exclusion criteria and in accordance with the medical recommendation of Drs. [name], and Drs. [name] or [name]. [name] will also encourage potential research participants to read the informed consent and take several days to discuss participation with friends and family before agreeing to enter the study. Drs. [name], [name], and [name] will explain to the potential participant that the initial enrollment involves a series of pre-experiments and 80 step/stand training sessions and the results are necessary to determine if they are an appropriate candidate for the surgical component of the study. Participating in the initial portion of the study does not guarantee their eligibility for surgical implantation and epidural stimulation.

The screening informed consent will be written in at an 8th-grade language level and will contain information on all evaluations to be performed as well as contact information should the research participant or his/her associates have any further questions. The original signed informed consent and two copies will be kept in [name] office.

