These individuals will not be concurrently enrolled in any other experimental studies unless approved by the principal investigator. Each research participant will be given a coded identification number to designate all evaluations. We will retain the data for reporting to granting agencies even when the individual is not eligible for the study. This data will be stored by the coded identification number without information identifying the individual.

We will evaluate the research participants for: 1) functional neurophysiological assessment (FNPA); 2) somatosensory evoked potentials (SEP); 3) sympathetic skin responses (SSR); 4) efferent motor activity during standing; 5) efferent motor activity during stepping; 6) reflexes during supine, prone, sitting and standing; 7) bladder function; and 8) cardiovascular function. Each of these measurements will take between 1 and 4 hours. The FNPA, SEP and SSR will be performed while the research participant is lying supine on a mat. The efferent motor assessments will be performed in the body weight support treadmill with the assistance of trainers at the hip and at each leg.

We will assess metabolic parameters, inflammatory markers, complete blood count, bone density and health markers, blood glucose control and drug toxicity panel. A trained

technician will draw a venous blood sample. Participants may undergo a 12-hour fast the night before, including no food or drink including alcohol or caffeine (water is permitted). A comprehensive drug screen by urinalysis will be done to assess the use of illicit drugs. These blood and urine analyses may be repeated periodically throughout the course of the study. A blood sample will be stored for batch processing at the end of the study (for participants that complete the screening process).

After completion of these evaluations, participants will undergo 80 sessions of step/stand training. We will repeat experiments after the completion of the 80 training sessions to quantify that no motor pattern changes are achievable with locomotor training alone. Drs. [name], [name] and [name] will meet to discuss the results of the preliminary testing and evaluate if the participant is eligible for surgical implantation for SCES.

FULL ENROLLMENT: Surgery + Epidural Stimulation + Training (2nd consent)

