If after evaluating the results, the study investigators determine that the participant is an appropriate candidate for surgery and epidural stimulation, the participants will be asked to sign an additional consent form. The surgical and epidural stimulation informed consent will be written in at a 8th-grade language level and will contain information on the surgery and all experiments to be performed as well as contact information should the research participant or his/her associates have any further questions. The original signed informed consent and two copies will be kept in [name] office.

The surgery will be performed at University Hospital to insert the epidural stimulating electrodes. The lead wires will be tunneled subcutaneously to exit 5 centimeters from the incision site. The implantable neurostimulator will be internalized and the connecting wires for the implanted electrodes will be tunneled under the skin and connected with the battery generator that will be placed in the abdominal area. We will repeat the experiments beginning at least 10 days after the surgery both with and without stimulation for 10 – 14 days. During the first two weeks after the surgery, the research participants may be hospitalized at Frazier Rehab Institute to monitor the incision site. We will also identify appropriate stimulation parameters for inducing stepping and standing in combination with manual assistance using body weight support on a treadmill (BWST).

Following discharge from inpatient or recovering at home the individuals will be seen in our lab on a daily basis for testing and locomotor training. We will evaluate the combination of epidural stimulation with manual step/stand training. This stage will be conducted over six-eight months. During training, the patients will be provided with epidural stimulation using the parameters defined in Stage 1. Testing may be performed weekly. The blood samples for metabolic parameters may be repeated prior to and after each training period. A blood sample will be frozen and stored in the laboratory for batch analysis for inflammatory markers, metabolic parameters, and markers for bone density.

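### The repeat testing after the 80 training sessions has its result written in advance, conflicts with the protocol's own account of training, and cannot show that no change is achievable

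*Protocol*

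**What the plan says.** Section D (Screening) evaluates participants, gives them 80 sessions of step/stand training, and then repeats the experiments "to quantify that no motor pattern changes are achievable with locomotor training alone". In the next sentence the investigators "will meet to discuss the results of the preliminary testing and evaluate if the participant is eligible for surgical implantation for SCES". Earlier in the same section, candidates are told that "the results are necessary to determine if they are an appropriate candidate for the surgical component of the study". The Full Enrollment text opens with "If after evaluating the results, the study investigators determine that the participant is an appropriate candidate for surgery and epidural stimulation". None of these places names a variable, a threshold or a direction for the decision.

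Other sections describe training differently. The Background (section A) says that "brief standing with full weight bearing can be executed after weeks of stand training, again without SCES". The Objectives (section B) say: "We propose that locomotor training will result in generation of more effective standing and stepping efferent patterns". Section G, under Locomotor Training Intervention, has body weight support coming down across the 80 sessions as participants become able to carry more of their own weight.

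Section F plans ten participants, and the Locomotor Training Intervention text gives n=10 for the 80 sessions. Section j states that no statistical comparison will be made and that the study is an unpowered proof of principle. Success is judged against the best performance seen in earlier patients who were only trained (section A and the end of section G).

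**The concern.** There is no concurrent control group. The before-and-after comparison over the 80 sessions is therefore the only evidence from the study's own participants on what training does without stimulation. If its purpose is to confirm that training does nothing, the reader loses a neutral estimate of the very quantity needed to attribute later gains to stimulation. The word *achievable* goes further still: it claims impossibility, not merely that nothing was seen.

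The same results also inform who is implanted. If that decision depends in any way on motor change, a training-alone result shown only for implanted participants would describe a group chosen partly on that result.

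**Working it through.** **No figure to reproduce.** The protocol gives no sample-size calculation, margin, error rate or expected change for this comparison. The check is a comparison of texts plus one exact binomial calculation.

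**Step 1: the texts side by side.**

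| Place | What training without stimulation is expected to do |
|---|---|
| Section D, Screening | No motor pattern change is achievable |
| Section A, Background | Brief full weight-bearing standing after weeks of stand training |
| Section B, Objectives | More effective standing and stepping efferent patterns, credited to locomotor training; stimulation has its own sentence |
| Section G, Locomotor Training Intervention | Weight bearing during stepping rises over the 80 sessions |

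The screening tests include efferent motor activity in standing and stepping, so the Objectives and the screening aim concern the same kind of outcome.

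**Step 2: could ten participants support the claim?** Inputs: n = 10 (sections F and G) and the result most favourable to the claim, 0 of 10 changing. Assume that change in each person is classified without error and that participants are independent.

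- One-sided 95% upper limit: solve (1 − p)^10 = 0.05, so p = 1 − 0.05^(1/10) = 0.2589, or 25.9%.
- Two-sided 95% interval, upper end: p = 1 − 0.025^(1/10) = 0.3085, or 30.8%.
- Chance of seeing 0 of 10 if the true rate is 10%: 0.90^10 = 0.349.
- Chance of seeing 0 of 10 if the true rate is 20%: 0.80^10 = 0.107.

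So if one person in ten truly changes with training alone, a study of this size sees no changer about 35% of the time. The denominator would be larger if more people complete the 80 sessions than are implanted, but the upper limit stays above zero for any finite number.

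**Step 3: the link to the implant decision.** The three statements quoted above make the screening results an input to candidacy. Those results also cover neurophysiological screening, evoked potentials, reflexes, bladder and cardiovascular function and laboratory tests, with MRI and quality of life added under Stage 1A. The text does not say which of them decides. If the decision ignores motor change, no selection on the training-alone result follows. If it uses motor change, selection follows, in a direction the text does not give.

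**The case against.** Several arguments on the other side have force.

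*Motor pattern* can be read narrowly, so that bearing more weight need not count as a change in pattern. That softens the conflict with the Background and section G. It does not remove the conflict with the Objectives, which speak of efferent patterns. It can be said that the Objectives describe training combined with stimulation. The overall aim does, but the quoted sentence credits locomotor training.

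Two Background statements look like further contradictions and are weak ones. That the spinal networks "after minutes of manual assistance, can generate a series of independent steps" describes an effect within minutes, and that individuals "can execute independent steps using a body weight support system on a treadmill (BWST) using manual assistance without epidural stimulation" describes what can be done with assistance. Neither is a change produced by weeks of training, and the point does not rest on them.

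A reader might infer that people who improve are refused implantation, so that part of any later gain over the post-80 test is regression to the mean. The protocol does not support this. It never says that low or unchanged values are selected, and it does not name the post-80 test as the reference for gains. Its success criterion is historical best performance. A size could be given only by assuming both a selection rule and a test-retest correlation, and with no selection on motor level the artefact is zero.

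A reader might also infer that the training-alone effect is fixed at zero by construction. It is not. Stage 1A measures before the 80 sessions and again after them, and section D retains data from people found ineligible.

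Finally, section j calls the study an unpowered proof of principle. That excuses the lack of a test, but it makes a universal negative harder to support, not easier.

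**Conclusion.** The point holds for the wording of the aim and for what may be concluded from it. Section D presupposes the result of the study's only within-person comparison of training alone, and sections A, B and G say or expect otherwise. Even the most favourable outcome, 0 of 10, leaves a true change rate of up to 25.9% compatible with the data (exact one-sided 95% limit, ten completers, error-free classification).

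The selection concern is conditional. It arises only if the implant decision uses motor change and the training-alone result is shown for implanted participants alone. The protocol settles neither, so the effect may be zero and no figure should be attached to it. This calls for correction of the text and the reporting; it does not show that the planned measurements are unusable.

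**What to change.** 1. In section D, restate the purpose of the repeat testing as: *estimate the change in standing and stepping motor activity after 80 sessions of training alone*.
2. Report that change for everyone who completes the 80 sessions, implanted or not. Section D already keeps the data of people found ineligible.
3. Do not conclude that no change is achievable with training alone, whatever is observed.
4. Reconcile section D with the Background, the Objectives and the Locomotor Training Intervention text, so that the protocol gives one account of what training alone is expected to do.
5. Show the post-80 values and the post-surgery stimulation-off values side by side where both exist. Replacing the first with the second is not advised: the later test follows surgery and a training gap of at least 10 days and falls in a period that mixes testing with and without stimulation. It is also not firmly planned, since section D says the experiments will be repeated and Stage 1C says they may be.

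The cost is small: a change of wording, slightly more reporting from data already being collected and kept, and a less favourable statement about training alone. Which eligibility rule should govern implantation is a clinical matter and is not addressed here.
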